Delirium occurrence rates for hospitalized older adults range from 29-64%. Although 30-50% of delirium is preventable, it frequently goes unrecognized until acute and potentially devastating. The Hospital Elder Life Program (HELP) is a multidimensional clinical strategy that is effective in preventing delirium, but labor intensive. This randomized controlled study will test an innovative method to implement the HELP approach: a tablet-based digital avatar that can see, hear, and talk with a patient using speech-to-text technology. The avatar platform has already been validated at Jamaica Hospital in a previous study in 2016: “GeriJoy: The Use of an Avatar Virtual Service Animal to Improve Outcomes in Hospitalized Older Adults” as well as in multiple published studies to effectively provide psychosocial support to older adults across varied clinical settings. This study will focus on discerning the relative impact of implementing HELP through this technology. Participants aged 65+ will be randomly assigned to receive one of the following interventions in addition to usual care throughout their hospitalization: 1) an avatar delivering HELP protocols and socialization; or 2) no intervention beyond usual care. Participants will be assessed by the investigators upon admission to the study and reassessed upon 24-hour discharge notification using the Short Portable Mental Status Questionnaire (SPMSQ), Memorial Delirium Assessment Scale, and Short CAM (Confusion Assessment Method). Based on patient medical records of sedation, restraints and incidence of falls and delirium, pre- and post-assessment scores will be compared using paired t-tests to determine outcomes among the groups. If the avatar is effective in improving outcomes by providing HELP interventions, the number of patients who benefit from HELP could increase greatly due to technology-enabled cost efficiencies, and protocol and data collection standardization across many sites.

Specific aims/hypotheses

For hospitalized older adults, will the use of an avatar delivering HELP protocols...

1. decrease delirium incidence and severity,
2. decrease falls and falls with injury,

..more than usual care?

Background and significance

Delirium strikes more than 5 people every minute, totaling over 2.6 million people annually in the U.S. (U. S. Department of Health & Human Services, 2011). It is under-recognized, leading to inappropriate use of sedation, sitters, and even restraints in the hospital setting (Adams & Kaplow, 2013; Harding, 2010). Delirium contributes to falls, cognitive decline, disability, morbidity, and mortality, increasing health care costs over \$164 billion a year (Inouye, Westendorp, & Saczynski, 2014; Labella, Merel & Phelan, 2011; Leslie & Inouye, 2011). Delirium can also initiate a “cascade of events” leading to an overall decline in function and independence (Fong, Tulebaev, & Inouye, 2009). These risks are greatest among older patients with limited English comprehension, low health literacy, and socioeconomic disadvantage (Tow, et al, 2016). Acute delirium may become chronic and have serious permanent sequelae (Fong, Tulebaev, & Inouye, 2009).

HELP is based on a geriatric assessment and integrates trained volunteers with hospital nursing staff to deliver protocols tailored to patients’ individual needs. The protocols target delirium risk factors including orientation, activities, mobilization, vision, hearing, hydration, nutrition, and natural sleep. Use of the tailored protocols is tracked daily for quality assurance. HELP is used in more than 200 hospitals worldwide and prevents delirium, cognitive and functional decline, falls, sitter use, institutionalization, and reduces length of hospital stay (Inouye, Bogardus, Baker, et al., 2000; Rubin, Williams, Lescisin, et al, 2006; Rubin, Neal, Fenlon, et al., 2011). Although HELP is cost effective, it requires extensive training and monitoring of a large team of volunteers, which can deter adoption, especially in safety net facilities that serve patients at highest risk (Rubin, Neal, Fenlon, 2011; Caplan & Harper, 2007).

This study will measure the effectiveness of implementing a subset of the HELP protocols using a novel type of relational agent, which is a technological entity capable of building social relationships with patients (Wang & Osborne, 2017). The relational agent platform, called “care.coach,” is provided by a California-based company founded by researchers from the Massachusetts Institute of Technology, and has been shown in multiple published studies to effectively provide psychosocial support through conversation and socialization with older adults in varied clinical settings (Machesney, Wexler, Chen & Coppola, 2014; Demiris, Thompson, Lazar & Lin, 2016; Chi, Demiris, Thompson, Lazar & Lin, 2016; Wexler, Drury & Pollak, 2016; Wexler, Drury & Pollak, 2017a; Wexler, Drury & Pollak, 2017b; Wang, Luxenberg & Morey, 2016; Chi, Sparks, Lin, Lazar & Thompson, in press). Uniquely, the relational agent is embodied as an animated animal displayed on a tablet device. This “avatar” represents a real-time fusion of human and software intelligence, powered by a live, 24x7 staff of health advocates who see, hear, and speak with each patient through the avatar, and who are guided by software algorithms to implement clinical protocols. Because the team is distributed across the world, they can cost-effectively provide unlimited compassionate psychosocial support, conversation in English and Spanish, and supervision: typically, when used for inpatient care, 1-6 hours/patient of direct attention, depending on patient need/risk, across 60-80 “check-ins” per 24 hours.

A study was conducted at JHMC in 2016 which enrolled 95 patients, of which half had a care.coach avatar. Patients were enrolled from 3 inpatient medical-surgical units. The avatar was used as a social conversational agent. The study found that patients who had the avatar experienced less delirium, less loneliness and experienced fewer falls (Wexler, Drury, Pollak, Scher, Iovino, Narducci, & Wang, in press).

Unlike common digital assistants such as Apple’s Siri that are limited by simplistic artificial intelligence and poor understanding of the speech of frail older adults, the care.coach avatar connects one human being to

another through an engaging animated dog or cat that responds to touch and demonstrates emotions appropriate to the conversation or other interaction state, e.g. through facial expressions, bodily reaction to touch, heart symbols, tears, sleeping, snoring, etc. Conversations and observations about the patient's state are automatically recorded and referenced in future interactions, providing both continuity in the growing relationship and quality control in the delivery of clinical protocols. In addition to conversation, the avatar can also display photos, play music, and read or pray with the patient. The staff undergo extensive non-medical training and for this study will also complete the HELP online training for volunteers.

The software system guiding the staff can be programmed to deliver complex sets of protocols, and has previously been used to implement coaching programs for managing multiple chronic conditions at home (Wang, Luxenberg & Morey, 2016), as well as in our prior exploratory work for preventing falls (e.g. through frequent toileting checks) and delirium (e.g. through simple re-orientation tasks) in the hospital. For this study, the system will be programmed to deliver a robust suite of adapted HELP volunteer protocols including re-orientation, vision/hearing aid checks, hydration and meal consumption encouragement, cognition and attention assessment for early delirium detection, and so on, including an automatic guidance and triage protocol for when to phone the nurses station (e.g. if a bed-bound patient is getting out of bed or tugging on IV lines). If the avatar is effective in improving outcomes by providing HELP interventions, the number of patients who benefit from HELP could increase greatly due to 1) the low cost and ease of deployment of the avatar platform, not only enabling hospitals that have yet to secure adequate budget and staff for a typical HELP program to begin seeing HELP benefits/outcomes data by deploying this technology-enabled variant, but also enabling existing HELP sites to easily expand coverage to nights and weekends, and to additional hospital units and patients, and 2) the ability of the avatar to standardize best practices and automate data collection and reporting (e.g. all survey instruments can be administered by the avatar itself), enabling large scale, highly consistent data aggregation and outcomes reporting across many such HELP sites.)

Study design: This randomized controlled trial will compare outcomes on delirium, falls, sitter utilization (1:1's) and restraints between the two study groups: HELP-protocolized avatars, and usual care. Each day of the study, enrollment of subjects will proceed with randomization of each subject between groups (the randomization primarily effects delirium data, which is assessed by subject) until there are no more available intervention devices. However, falls and other unit-level grouping are non-randomized (see below).

Sample Size: A total of 3,650 patients (avatar and usual care) are expected to be enrolled at JHMC over the course of two years, based on an estimated average length of stay of 4 days.

Study Units: Patients will be recruited from the following units at JHMC: 3S, 3N, 4S, IMCU, 5N, 6S, and Hospice. Because the hospital only collects/reports unit-by-unit quarterly falls data, we will take the following measures to ensure that falls data collected for study purposes are a valid indicator of possible intervention effect:

- There are expected to be protocol and technical adaptations made during the first quarter of the study, and the study will not begin enrolling subjects exactly at the start of a calendar quarter. Therefore, the first calendar quarter of falls data is not intended to provide useful data regarding unit-level falls outcomes, and enrollment of patients may be performed on select units by convenience.
- Starting on the first day of the first full calendar quarter, a unit-equitable enrollment protocol will be implemented in which one or more of the study units at any time may be formally designated for active subject enrollment, and such designated study units will have their enrollment numbers monitored and rounding adjusted as needed to ensure that, on average, each designated unit receives a similar number of intervention patients at any time. Which units are designated or not designated for enrollment may be changed at the start of each calendar quarter to compare the effect of the intervention and to control for annual changes in fall rates. Research assistants will not enroll any patients on units not designated for enrollment, but will continue to round currently enrolled patients until they are dis-enrolled.

Sample inclusion and exclusion criteria: All patients over age 65 on the pilot units who can provide informed consent or who have a proxy who can provide informed consent will be assessed by the investigators. Those who consent will be randomly assigned to one of the two treatment conditions unless they meet any of the exclusion criteria: a.) aggression or combativeness with intent to harm self or others, b.) alcohol or drug withdrawal, c.) severe hearing impairment and simultaneous severe vision impairment, despite assistive devices, d.) cannot verbalize fluently in either Spanish or English, e). on 1:1;if a study subject is put on 1:1 during the duration of the study, he/she will be unenrolled from the study, f) expected to be discharged within the next 24 hours.

Instruments

Pre- and post-intervention:

1. Short Portable Mental Status Questionnaire
2. Short CAM (Confusion Assessment Method) – also conducted during each daily round
3. Memorial Delirium Assessment Scale – if CAM screens positive

Statistical analyses: Demographic variables including age, gender, education, race/ethnicity, and living arrangements will be collected to determine equivalency of study groups. Pre-and post-assessment scores will be compared using paired t-tests to compare means at baseline and at hospital discharge within each group, and between groups. All data will be analyzed using the Statistical Package for Social Sciences software (SPSS, Inc. Chicago, IL). Statistical significance will be defined as $p \leq 0.05$.

Additional Information

Photos of Avatar

Figure D.8.1: A hospitalized older adult in South Carolina enjoys the company of an avatar as it plays music and shows a photo. A “fisheye lens” mounted to the top of the avatar device enables wide-angle visual monitoring, to enable appropriate reaction by the avatar to not only the patient’s facial and body language cues, but also any dangerous unassisted transfers, tugging on IV lines, etc. To help with re-orientation, the window behind the avatar reflects the actual weather report, and the lighting of the avatar’s environment reflects day or night status. A video showing the patient talking to the avatar and singing along is available at <https://www.youtube.com/watch?v=WfWjazOmKUk>

Figure D.8.2: The avatar is available in dog or cat form, depending on patient preference. Patients name their avatar as further personalization. On the left, the dog avatar is showing a photo from a web-based Family Portal, which helps with engagement and reminiscence.

Avatar Staff Training

The health advocates who staff the avatar system must each complete the following screening mechanisms and training certifications (or their equivalent as deemed by care.coach, as specific training courses and providers become outdated/available from time-to-time), through several online learning platforms, over the course of approximately 65 hours:

1. care.coach psychometric, technical, skills-based & face-to-face interview assessment
2. InfoCubic international background check
3. Registered Nurses' Association of Ontario delirium, dementia and depression course
4. National Institutes of Health privacy & ethics course for human subjects research
5. Partners Healthcare basic motivational interviewing class
6. care.coach technology, patient support, information security, and job shadowing training

The qualification process is very stringent, and the proportion of health advocate job applicants who successfully complete all the required certifications and are hired is only about 1%. Health advocates also receive ongoing training and professional development after hiring, including programs such as the Alzheimer's Association dementia care course (essentiALZ®).

For the proposed project, each health advocate will also complete the HELP volunteer training, and a one-hour module using resources from the American Delirium Society and American Nurses Association .

Clarification Regarding Data and Safety Monitoring Plan (DSMP)

In reference to the DSMP, under the physical risk mitigation section, the spirit and effectiveness of the described mitigation techniques will be preserved, but as of December 28, 2018, we are aware of the following minor technical and practical issues that affect the details of implementing the described mitigation techniques:

- The voice recording that plays automatically when a device is unplugged is standardized to say that the device is an important healthcare tool that needs to be kept plugged in to power, but the comment about “the device must be sanitized before placing it back into its designated storage cabinet” may instead be implemented with the following variations:
 - The reminder to sanitize the device may be performed by the avatar itself as part of the dis-enrollment and/or enrollment protocol, combined with a visual reminder on a label on each device.
 - For many technical and practical reasons, the avatar is now designed to stay online, plugged in to power even while on standby between patients. So instead of going back to a storage cabinet it will go to a charging area in [name] office, and a visual reminder about this will be placed on a label on each device.
- Due to potential technical limitations of the EHR/Epic integration the practical nature of the varied data in each patient record, we may not be able to rely on specific Epic data for each patient to indicate suitability for self-ambulation protocols, and we may never be able to push/write to the patient record. Therefore, the spirit of the risk mitigation techniques may be alternatively implemented as follows:
 - Instead of relying on Epic data, we may rely on nursing judgement when the avatar is verbally told to place the patient on a self-ambulation encouragement protocol.
 - Instead of confirming the assignment of a self-ambulation protocol to a patient through an Epic integration, we may phone call the nursing station to confirm.

References

Chi, N., Sparks, O., Lin, S., Lazar, A., Thompson, H.J., Demiris, G. (In press). Pilot testing a digital pet avatar for older adults. *Geriatric Nursing*.

Harding A.D. (2010). Observation assistants: sitter effectiveness and industry measures. *Nurs Econ.*, 28 (5): 330–336.

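### The severity half of aim 1 is compared only at baseline and discharge, so delirium that starts and clears during the stay is left out, and patients who die or are unenrolled have no closing score

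*Combined protocol and SAP*

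**What the plan says.** The Specific aims section asks whether the avatar will "decrease delirium incidence and severity" more than usual care does. The opening summary fixes two assessment times ("Participants will be assessed by the investigators upon admission to the study and reassessed upon 24-hour discharge notification") and lists the SPMSQ, the MDAS and the Short CAM at both, without conditions. It also names medical records as a source for delirium incidence.

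The Instruments list puts all three scales under a pre- and post-intervention label, with two qualifications. The Short CAM is "also conducted during each daily round". The MDAS is given "if CAM screens positive". Whether a positive CAM on a daily round counts as that trigger is not stated.

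The Statistical analyses section uses paired t-tests to "compare means at baseline and at hospital discharge within each group, and between groups". No other use of the daily CAM results is described.

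Two further provisions bear on who has a closing score. The Study Units section recruits from "3S, 3N, 4S, IMCU, 5N, 6S, and Hospice". The eligibility section unenrols any participant who is put on 1:1 during the study. No section says how a death, an unenrolment or a missing closing score is handled in the analysis.

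**The concern.** A delirium-prevention trial is mainly interested in episodes that begin after entry. If severity is compared only at the two ends of the stay, an avatar that makes mid-stay episodes milder gets no credit for it.

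The second issue is selection after randomisation. A paired test uses only patients with both scores. The Background section states that "Delirium contributes to falls, cognitive decline, disability, morbidity, and mortality", and Hospice is a study unit, so deaths before discharge have to be provided for. The Background also ties unrecognised delirium to sitter use, and the Study design section lists 1:1 use as an outcome. Unenrolment on 1:1 is therefore plausibly related to delirium. Because the avatar staff can phone the nurses' station about unsafe behaviour, it could also differ between arms. Randomisation does not protect a comparison restricted in this way.

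**Working it through.** **Step 1. What enters the MDAS comparison.** The text allows three readings. A: MDAS at entry and closing only, when the CAM at that time is positive (Instruments, narrow reading). B: MDAS at any positive CAM, daily rounds included (Instruments, wide reading). C: MDAS at entry and closing regardless of CAM (opening summary).

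| Patient | A | B | C |
|---|---|---|---|
| CAM negative at entry, positive mid-stay, negative at discharge | no MDAS | in-stay MDAS exists, but no baseline or discharge value | both values exist; neither is taken during the episode |
| CAM negative at entry, positive at discharge | discharge value only | discharge value, plus any from positive daily rounds; no baseline value | full pair |
| Dies, or unenrolled on 1:1 | no discharge value | no discharge value | no discharge value |

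In the first row the readings differ on whether the episode is graded. They agree that its severity does not enter a comparison of baseline with discharge. In the third row all three agree that there is no pair.

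**Step 2. The plan's own figure.** The Sample Size section gives 3,650 patients over two years from a 4-day average stay. One place turns over 730 / 4 = 182.5 times, so 3,650 / 182.5 = 20 concurrent places. The documents do not state that number, so 3,650 can be solved backwards but not reproduced. It serves below only as a denominator.

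**Step 3. Illustration of ungraded episodes under reading A.** The summary gives a delirium occurrence range of 29-64%. The share of episodes that clear before discharge is not given; 25-75% is assumed.

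- At 29%: 3,650 × 0.29 ≈ 1,058 patients; × 0.25 ≈ 265 and × 0.75 ≈ 794 without a severity value.
- At 64%: 3,650 × 0.64 = 2,336 patients; × 0.25 = 584 and × 0.75 = 1,752.

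The occurrence range may include delirium already present at entry, so these are not estimates of the loss.

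**Step 4. Illustration of selection.** Let p be the true delirium rate, and d and n the shares without a closing score among delirious and non-delirious patients. The observed rate is p(1−d) / [p(1−d) + (1−p)(1−n)]. Take p = 0.29 in both arms and n = 0.05 (n and d assumed).

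- d = 0.20: 0.232 / (0.232 + 0.6745) = 25.6%.
- d = 0.30: 0.203 / (0.203 + 0.6745) = 23.1%.

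If d is 0.20 in one arm and 0.30 in the other, a difference of 2.5 points appears with no true effect, and its direction depends on which arm loses more. If d is 0.20 in both arms, no difference appears, but both rates are understated (25.6% against 29%).

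**The case against.** The strongest reply is that the daily Short CAM already detects delirium that clears, and that the MDAS line directly below it can naturally be read as applying to any positive CAM. This stands in part. A reader might infer that cleared delirium is never graded, or that its incidence is lost. The documents support neither: grading depends on an unresolved reading, and incidence is recoverable from the daily CAM and the medical records. What the reply does not reach is the analysis, which still uses only baseline and discharge.

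Other strong readings also fail:

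- **Short notice.** The discharge notice may be only a scheduling trigger, since the Statistical analyses section refers simply to discharge. The criterion excluding patients expected to leave within 24 hours also removes some early exits. It is not established that everyone leaving at short notice lacks a score.
- **Transfer.** Nothing says follow-up ends when a patient changes unit.
- **Timing.** Nothing says delirium has usually cleared by discharge. The Background section says acute delirium may become chronic.
- **Who is missing.** That the missing patients are the most delirious is an inference from a general statement about mortality. As Step 4 shows, equal loss in both arms gives no spurious difference. Unequal loss is possible but not shown.
- **Hospice.** No section supports the view that scores there mean something different, so a separate Hospice analysis does not follow.

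**Conclusion.** The point holds in a limited form. The stated analysis does not measure the severity half of aim 1 for episodes that arise after entry and clear before discharge, whichever reading of the MDAS condition is taken. Patients who die or are unenrolled on 1:1 have no discharge score and leave the paired test, and no rule covers them. This is a choice of endpoint timing combined with a gap on missing data, not an arithmetic error.

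The size cannot be computed from the documents. The counts in Step 3 and the 2.5 points in Step 4 rest on assumed shares and show only what could happen. A reader might apply an assumed 5-15% without a closing assessment to 3,650 and obtain about 183 to 548 patients. That would count missing closing scores of any kind on an unsupported share, and it does not measure the loss of severity data.

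**What to change.** 1. State that any CAM-positive daily round triggers an MDAS, and reconcile the opening summary with the Instruments list on whether the MDAS is conditional.
2. Compare arms on delirium incidence from all post-randomisation CAMs, stating how patients already CAM-positive at entry are counted.
3. Define severity as the highest post-randomisation MDAS, with a pre-specified lowest value for patients who are never CAM-positive. All randomised patients with at least one post-entry round are then included up to death, discharge or unenrolment. Report by arm the number with no post-entry round.
4. Keep the discharge SPMSQ comparison as secondary, and report by arm the number of missing closing scores and the reasons. The last daily round cannot stand in for the closing assessment, because the only scale marked as done on daily rounds is the Short CAM, so it gives no SPMSQ.

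The cost is protocol wording and some additional MDAS administrations by staff who already make the rounds. Two limits remain. Peak severity depends partly on how many rounds a patient has, so length of stay should be reported by arm. Observation still stops at death or unenrolment, so selection is reduced, not removed.

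### The source of incident delirium is not settled: the summary points to medical records, where detection could differ by arm, while the daily Short CAM has no analysis role

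*Combined protocol and SAP*

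**What the plan says.** The first item under Specific aims/hypotheses is a reduction in delirium incidence and severity. The documents point to more than one source for it.

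- **Medical records.** The opening summary introduces the outcome comparison with "Based on patient medical records of sedation, restraints and incidence of falls and delirium".
- **Direct assessment at entry and discharge.** The same summary says "Participants will be assessed by the investigators upon admission to the study and reassessed upon 24-hour discharge notification", using the SPMSQ, the Memorial Delirium Assessment Scale and the Short CAM. No arm restriction is stated.
- **Direct assessment each day.** The Instruments list says the Short CAM is "also conducted during each daily round". The Memorial scale follows "if CAM screens positive".
- **Level of the data.** Study design says "the randomization primarily effects delirium data, which is assessed by subject".

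Statistical analyses compares only pre- and post-assessment scores, at baseline and discharge. The daily CAM does not appear there, and incident delirium is not defined.

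On detection, the summary says of delirium that "it frequently goes unrecognized until acute and potentially devastating". Background and significance lists, among the avatar's functions, "cognition and attention assessment for early delirium detection", "including an automatic guidance and triage protocol for when to phone the nurses station". The comparison arm receives usual care alone.

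**The concern.** Early detection of delirium is a stated function of the intervention, and the chart is a stated source of the outcome. If the avatar brings nurses to the bedside more often, or passes on what it observes, a true episode has a better chance of being charted in the avatar arm than in usual care. Randomisation does not remove this, because the allocated treatment itself causes the difference.

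The bias would raise charted delirium in the avatar arm, so it works against the intervention. A real reduction could shrink, vanish or change sign. With no true effect, the avatar could appear to cause delirium. Analysis cannot repair this afterwards if recognition rates by arm are unknown. The daily Short CAM, apparently done in both arms, could avoid the problem but has no assigned role.

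**Working it through.** **Inputs from the documents**
- Delirium occurrence 29–64% and preventable share 30–50% (summary). A preventable share of 30–50% corresponds to true ratios of 0.70 to 0.50. These are used for illustration only, since the plan states no target effect.
- Total enrolment 3,650 over two years with a mean stay of 4 days (Sample Size). As throughput, 3,650 × 4 / 730 days = 20 patients enrolled at any time. The plan does not state that 20, so the figure is consistent but cannot be reproduced independently. No power calculation is given.
- Significance at p ≤ 0.05 (Statistical analyses).

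**Assumptions not in the documents**
- 1:1 allocation, so 3,650 / 2 = 1,825 per arm, and a two-sided test.
- Chart recognition of 50% in usual care and 50–80% in the avatar arm.
- No false-positive charting.

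**Formulas**
- Charted rate = true rate × recognition.
- Apparent ratio = true ratio × (avatar recognition / usual-care recognition).

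**Case 1: true incidence 29% vs 0.29 × 0.70 = 20.3%.** Usual care is charted at 0.29 × 0.50 = 14.5%.

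| Avatar-arm recognition | Charted, avatar arm | Apparent ratio | Chance of p ≤ 0.05 |
|---|---|---|---|
| 50% | 0.203 × 0.50 = 10.2% | 0.70 | 98%, favouring avatar |
| 60% | 0.203 × 0.60 = 12.2% | 0.84 | 54%, favouring avatar |
| 70% | 0.203 × 0.70 = 14.2% | 0.98 | 4%, favouring avatar |
| 80% | 0.203 × 0.80 = 16.2% | 1.12 | 31%, against avatar |

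**Case 2: no true effect, 29% in both arms.** Recognition of 50% vs 60% gives 14.5% vs 17.4%, an apparent ratio of 1.20. The chance of a significant result against the avatar is 67%.

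**Case 3: true ratio 0.50.** Avatar-arm recognition of 60%, 70% or 80% gives apparent ratios of 0.60, 0.70 or 0.80.

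**Break-even.** The recognition ratio that cancels the effect is 1 / true ratio: 1 / 0.70 = 1.43 for a 30% reduction and 1 / 0.50 = 2.0 for a 50% reduction. This does not depend on incidence.

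**Lower incidence and recognition.** Occurrence may include delirium already present at admission, so incidence could be below 29%. Assume 20%, with recognition of 40% vs 50%:
- No true effect: 8.0% vs 10.0%, ratio 1.25, z = 2.11, p = 0.035.
- True ratio 0.70: 8.0% vs 7.0%, ratio 0.875, z = −1.15, p = 0.25.

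With equal recognition in both arms, the apparent ratio equals the true ratio and this bias is zero. The same holds for a Short CAM done identically in both arms, even if it misses some episodes.

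**The case against.** The strongest reply is that charts may not be the operative source at all. The summary sentence opens with medical records, but what it then compares is pre- and post-assessment scores. Investigators do the Short CAM at entry and discharge with no stated arm restriction, the Instruments list contains no chart diagnosis, and Study design describes delirium as assessed by subject. This stands in part: the source is ambiguous. However, no other passage says where incidence comes from, and a discharge score does not identify an episode that arose and resolved during the stay.

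The second reply is that a link from the avatar to the chart is not documented. A reader might infer that avatar-arm delirium will be charted more completely and that the comparison is therefore biased. The documents do not support that as fact. The two examples of a call to the nurses are safety events (getting out of bed, pulling at IV lines). Nothing says that a failed cognition check is phoned in or charted, and the DSMP clarification says the system might never be able to write to the patient record. What remains is verbal contact with nurses, which is a plausible route.

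Nor should the 60–80 check-ins per 24 hours be read as a trial schedule. Background and significance gives that figure as typical of the platform in inpatient care. If positive daily CAMs reach clinicians in both arms, the recognition gap would also narrow.

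Finally, the bias could not by itself create a false benefit, which limits its severity. The alternative has its own weakness: rater blinding is not mentioned, and a bedside tablet would ordinarily reveal the arm.

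**Conclusion.** The concern holds in conditional form. The source of incident delirium is undefined, and the only one named for it is open to detection that depends on the arm. If charts are used, recognition is likely to differ, and the effect would run against the avatar.

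The size cannot be known from the documents, because they give no recognition rates. Under the assumptions shown, a true ratio of 0.70 could appear anywhere from 0.70 (equal recognition) to 1.12 (50% vs 80%), and a recognition ratio of 1.43 removes it entirely. These figures illustrate sensitivity and do not predict the result.

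This should be fixed, because it touches the first aim and the remedy is cheap. It does not make the trial invalid: a per-subject research assessment is already planned, apparently for both arms.

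**What to change.** State one definition in the protocol and SAP:

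- Incident delirium is the first positive research Short CAM after a negative baseline CAM. Patients positive at baseline are left out of the incidence analysis.
- The CAM follows the same daily-round and discharge schedule in both arms.
- Study staff administer it in both arms, never the avatar. This must be explicit, because Background and significance says the avatar is able to administer all the survey instruments.
- Raters score it without access to avatar logs or alerts, and avatar assessments do not feed the endpoint.
- Chart delirium is kept as a secondary or descriptive measure of recognition, and the summary sentence is reworded to match.

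The cost is mainly wording, since the daily CAMs are already planned and no new visits are needed. There are two downsides. The incidence denominator falls by the number positive at baseline. Raters will also probably see the tablet, so knowledge of the arm could influence scoring, possibly in the avatar's favour. Blind raters where feasible and state the remainder as a limitation. Reporting chart delirium alongside helps here, because its likely bias runs the other way.
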